2.15.2 Safety Analysis

Adverse events (AEs) will be grouped by body system. The number and percentage of subject experiencing at least one AE of any type, AEs within each body system and AEs within each preferred term will be tabulated and listed. Separate summaries will be provided for all AEs, AEs by maximum severity, drug related AEs, severe adverse events (SAEs), and for AEs leading to withdrawal. All adverse events experienced by subjects will be collected from beginning of visit 1 through final study visit. Study subjects will be routinely questioned about adverse events at study visits. The study investigators will evaluate all subject reported and observed AEs. All untoward medical occurrences observed in subjects receiving the study drug will be recorded on the participants' adverse event worksheets by the study coordinator under the supervision of the principal investigator. AEs occurring pre-treatment, during active treatment and post-treatment will be summarized separately.

2.15.3 Handling of missing data:

Every effort will be made to collect complete data on each study day. With respect to safety evaluation, it is not planned to impute missing data.

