1.2 SPECIFIC AIMS

Hypotheses:

(1) Nebulized sodium nitrite will be well tolerated by adults with CF.

To determine the therapeutic potential of sodium nitrite for CF, we propose two specific aims:

Specific Aims:

Aim 1: Determine the safety of nebulized sodium nitrite administered in two doses to patients with CF.

Aim 2: Explore the effects of nebulized sodium nitrite on measures of lung function, exhaled airway nitric oxide, and bacterial burden.

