2.2 STUDY DESIGN AND METHODS

2.2.1 *Study Design*

A total of 35 subjects with a confirmed diagnosis of cystic fibrosis meeting all the eligibility criteria will receive the investigative drug, nebulized sodium nitrite. The starting dose of nebulized sodium nitrite is 45 mg for the first week to provide multiple dose safety data and subject tolerability prior to the observed escalation target dose of 90 mg for the remaining three weeks of the study.

Screening (day -28 to -2): Potential subjects will be recruited from the CF Center at Children's Hospital of Pittsburgh and/or the UPMC Comprehensive Lung Center (CLC). In these locations, individuals with CF are followed on a routine basis and are well known to the study investigators. Initial screening evaluations including urine pregnancy test (only on females of childbearing potential), physical examination, medical history, and clinical laboratory assessments will be conducted to determine study eligibilities during a routine clinic visit. If a patient has had the required screening laboratory assessments within the past 6 months, results of those tests will be used for screening purposes and only repeated if clinically significant abnormalities were identified. In addition, vital signs (pulse, non-invasive blood pressure measurement, temperature, respiratory rate and oxygen saturation) will be performed. Subjects who meet the inclusion criteria and none of the exclusion criteria will be entered into the study and baseline spirometry will be obtained with the study spirometer. If the participant is on inhaled antibiotics, Visit 1 will be scheduled 2-7 days after the participant initiates the next scheduled inhaled antibiotic. Subjects are to remain on the same inhaled antibiotic through the end of Visit 5. Remaining on the same inhaled antibiotic for more than one month is quite common in CF clinical care.

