5.5.4 Frequency of Monitoring

The Investigator will review subject safety data as it generated. The Investigator and the research staff will meet on a quarterly interval to re-evaluate study goals, subject recruitment, data coding and retention, documentation and identification of adverse events, complaints and confidentiality of subjects. There will be an evaluation of the progress of the research study, including assessments of data quality, time lines, participant recruitment, accrual, and retention. The Investigator will also review the outcome and adverse event data to determine whether there is any change to the anticipated benefit-to-risk ratio of study participation and whether the study should continue as originally designed or should it be re-evaluated and changed.

The iDSMB is expected to meet at least two times a year at the call of the Chairperson to review the progression of the study including patient enrollment, protocol compliance, and adverse event reports. An emergency meeting of the iDSMB may be called at any time by the Chair should participant safety questions or other unanticipated problems arise.

5.5.5 Adverse Event Reporting:

The study investigators will be responsible for detecting, documenting and reporting events that meet the following definition of an adverse event as defined below:

Adverse event. Any untoward medical occurrence in a clinical study; regardless of the causal relationship of the event with the investigational drug or study treatment(s).

Associated with the use of the investigational drug or study treatment(s). There is a reasonable possibility that the adverse event may have been caused by the investigational drug or study treatment(s).

Disability. A substantial disruption of a person's ability to conduct normal life functions.

Life-threatening adverse event. Any adverse event that places the patient or subject, in the view of the investigator, at immediate risk of death from the event as it occurred (i.e., does not include an adverse event that, had it actually occurred in a more severe form, might have caused death).

Serious adverse event. Any adverse event occurring at any dose that results in any of the following outcomes: death, a life-threatening adverse event, inpatient hospitalization or prolongation of existing hospitalization, a persistent or significant disability/incapacity, or a congenital anomaly/birth defect.

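### The planned adverse event summaries pool 45 mg and 90 mg into one active-treatment period, so events during home dosing have no by-dose summary

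*Combined protocol and SAP*

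**What the plan says.** Aim 1 in section 1.2 is to "Determine the safety of nebulized sodium nitrite administered in two doses to patients with CF". Section 2.2.1 gives the lower dose a safety purpose of its own: "The starting dose of nebulized sodium nitrite is 45 mg for the first week to provide multiple dose safety data and subject tolerability". It is followed by the "observed escalation target dose of 90 mg for the remaining three weeks of the study". Subjects who do not tolerate 90 mg on Day 7 may return to 45 mg and stay in the study (2.2.1, 2.6, 2.13.1, 2.14.2).

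Section 2.15.2 is the whole AE analysis. Events are tabulated by body system and preferred term, with further summaries for "AEs by maximum severity, drug related AEs, severe adverse events (SAEs), and for AEs leading to withdrawal". The only division by time is this: "AEs occurring pre-treatment, during active treatment and post-treatment will be summarized separately". Sections 2.5 and 5.5.2 repeat that sentence. No section plans an AE table by dose or says how an event is assigned to a dose.

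Section 5.5.5 defines the SAE concept by outcome: "Serious adverse event. Any adverse event occurring at any dose that results in any of the following outcomes". The list in 2.15.2 writes the same abbreviation after the word severe.

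**The concern.** Section 2.2.1 justifies the 45 mg week by the safety data it will yield, yet followed as written the plan has no AE table that reports those data separately. The dose-specific measurements on Days 0 and 7 cover the first dose at each level. Nearly all later doses are taken at home, where tolerability shows mainly through reported events, with spirometry and the CFQ-R at visits. Section 2.15.1 names cough and respiratory symptoms as the main events in comparable trials and says that they need not track bronchoconstriction. FEV1 therefore cannot stand in for them.

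At stake is whether a reader of the final report can see which dose a home-dosing event arose on. No sample size, primary result or stopping rule depends on it.

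**Working it through.** **The plan's own figure.** The AE analysis contains no numerical target. The plan's one statistical calculation (2.15.1: n = 33, null rate 0.06, alternative 0.06 + 0.14 = 0.20, one-sided 0.05, power 82%) reproduces. Rejecting at 5 or more of 33 gives an exact alpha of 0.0454 and power of 0.818. It does not bear on this point.

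**Planned exposure** (2.2.1, 2.10; twice daily, everyone escalates, no dropout):

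| | 45 mg | 90 mg |
|---|---|---|
| Days | 7 | 21 |
| Doses per subject | 7 × 2 = 14 | 21 × 2 = 42 |
| Directly observed by plan | 1 (Day 0) | 1 (Day 7) |
| Subject-weeks, 35 subjects | 35 × 1 = 35 | 35 × 3 = 105 |

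**What is assessed by dose**

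- FEV1 before dosing and at 30 and 120 minutes, Day 0 at 45 mg and Day 7 at 90 mg (2.13.1).
- Blood pressure, oxygen saturation and methemoglobin over the two hours after those same doses (2.2.1, 2.10).
- Intolerance criteria with separate consequences at each dose (2.6, 2.14.2).
- AEs: no division by dose (2.5, 2.15.2, 5.5.2).

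**What pooling hides.** The weekly risks below are assumptions, not figures from the documents. Let a be the weekly risk of a first event at 45 mg and b at 90 mg, independent across weeks. The pooled proportion with at least one event is 1 − (1 − a)(1 − b)³.

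- a = 2%, b = 12%: 1 − 0.98 × 0.88³ = 33.2%.
- a = b = 10%: 1 − 0.90⁴ = 34.4%.
- A pooled 30% fits a = 0%, b = 11.2%; a = b = 8.5%; or a = 20%, b = 4.4%.

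**Why percentages alone would not repair it.** With equal weekly risk at both doses, raw by-dose percentages still differ, because one column covers one week and the other three.

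- 5% per week: 5.0% against 1 − 0.95³ = 14.3% (pooled 18.5%).
- 10% per week: 10% against 1 − 0.90³ = 27.1%, a ratio of 2.7 with no dose effect.

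Dividing events by subject-weeks removes this distortion.

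**Why splitting by calendar week would not repair it.** Subjects who step down on Day 7 take 45 mg in weeks 2–4. The documents give no step-down rate. As an assumed range, borrow the 5%, 10% and 20% that 2.15.1 uses for FEV1-related discontinuation. Of the 105 subject-weeks in weeks 2–4, 5.25, 10.5 and 21 would then be at 45 mg and would be counted under 90 mg.

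**Period boundaries.** AE collection starts at Visit 1 (2.15.2), so the pre-treatment period is only the hours before the first dose. The synopsis gives 56 days of treatment. Follow-up is 14 days after treatment (2.4), and the last visit is Day 42 ± 5 (2.11), so dosing ends about Day 42 − 14 = 28. Fifty-six days would run past the latest possible final visit, Day 47. The active-treatment window cannot be defined until these passages agree.

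**The case against.** The strongest reply is that Aim 1 is already addressed by dose where the protocol puts most weight. FEV1 is the primary safety endpoint and is compared at each dose, the trial is sized on FEV1-related discontinuation, and acute hemodynamics, saturation and methemoglobin are tied to dose. This stands. A reader might infer that the plan cannot answer Aim 1 at all, or that AEs are its main evidence. The documents support neither. The gap is confined to AEs, chiefly those arising at home.

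Second, Aim 1 does not ask whether 90 mg is worse than 45 mg, and by-dose AE tables could not settle it. Dose is confounded with time and order, only subjects who tolerate 45 mg reach 90 mg, and there is no control. This also stands. The tables would be descriptive.

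Third, the pooling is by omission. AEs are also to be listed, and a split could be added at reporting. That is true if onset date and current dose are recorded, but without a written rule the handling of step-down time would be decided after the data are seen.

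Fourth, the weekly risks in the working are assumed, and the 2%/12% pair gives nearly the same pooled total as 10% at both doses. They show what could happen, not how large an effect will be. The 2.7-fold distortion belongs to a naive split that the plan does not contain.

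On wording, a reader might infer that serious AEs have no summary. That is too strong. The item is listed apart from maximum severity and carries the SAE abbreviation, so it is most naturally a slip for serious. Section 5.5.2 also requires a written account to the DSMB and IRB of serious, unexpected, treatment-related events.

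**Conclusion.** The point holds for the AE summaries. Following 2.15.2 exactly puts about 1 week at 45 mg, about 3 weeks at 90 mg and any step-down time into one period, although Aim 1 concerns two doses and 2.2.1 gives the 45 mg week its own safety purpose. AEs during home dosing therefore have no by-dose summary.

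The 1:3 exposure ratio comes from the schedule and assumes full escalation and completion. The pooled and by-dose percentages rest on assumed weekly risks. Nothing here affects the primary FEV1 comparison or the sample size, and nothing in the finding calls for showing the secondary endpoints by dose. The SAE wording is a separate editorial correction. The change is a free improvement, not a condition for the trial to proceed.

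**What to change.** In 2.15.2, with matching text in 2.5 and 5.5.2:

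1. Divide the active-treatment period by the dose most recently taken at AE onset: 45 mg before escalation, 90 mg, and 45 mg after step-down. For a same-day re-challenge on Day 7, events after the 90 mg dose and before the re-challenge count under 90 mg, and later events count under step-down.
2. Use as denominator the subjects who received at least one dose in that category. Report both the number of subjects with events and events per subject-week.
3. State that by-dose rates are descriptive, because dose is confounded with time and with tolerance of 45 mg and there is no control.
4. Change severe to serious in the SAE item, using the definition in 5.5.5.
5. Reconcile the synopsis treatment duration with 2.2.1, 2.4 and 2.11, then define the active-treatment window.

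The cost is analysis text and a few table columns. No subjects, visits or procedures are added. Confirm that the AE worksheet records onset date, with clock time on Day 7, and the current dose.

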Experimental Procedures (visit 1/day 0 (+/- 1day)): This visit will take approximately 5 hours. Subjects will arrive and complete the CFQ-R CF Questionnaire. Vital signs will be recorded and a physical examination performed, subjects will provide a sputum sample if able, and complete an oral wash specimen. The fractional excretion of nitric oxide (FENO) will be measured using a NIOX device, and baseline spirometry will be obtained. If subjects are unable to spontaneously expectorate sputum, then sputum induction will be done, followed by at least a 30 minute observation period because sputum induction is associated with temporary bronchoconstriction which might confound further measurements. The observation period will be omitted in subjects that spontaneously expectorated sputum. Next, an electronic nebulizer will be used to deliver 45 mg of nebulized sodium nitrite. Subjects will be monitored closely for the next two hours, including percutaneous measurements of oxygen saturation and methemoglobin levels, recorded at minutes 15, 30, 60 and 120, and noninvasive systemic blood pressure measurements every 15 minutes. Spirometry will be repeated at 30 and 120 minutes following nebulized sodium nitrite administration. If percutaneous methemoglobin measurements exceed 5%, they will be confirmed by venous blood measurement. If nebulized sodium nitrite is tolerated, then the subject will be dispensed an 8 day supply of 45 mg nebulized sodium nitrite dosed two times daily and discharged from the CTRC, CHP or the Emphysema Research Center in Montefiore. If the 45mg dose of nebulized sodium nitrite is not tolerated, the subject will be observed until stable and then discharged from the CTRC, CHP or the Emphysema Research Center in Montefiore.

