2.7.4 Drug Administration

The route of administration is by nebulization. It is anticipated that each nebulization will take approximately 10 – 15 minutes to deliver the dose. All doses specified in the protocol are the amounts of nebulized sodium nitrite placed into the nebulizer cup. We will be using Aerogen Solo nebulizers, as was done in the study by Simon, *et al* (17).

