2.11 SCHEDULE OF ACTIVITIES

Study Phase	Screening	Treatment				Follow-Up Monitoring
Visit Type	Outpatient	Outpatient				
Study Day	day -28 to -2	(visit 1) day 0 - +/- 1 day	(visit 2) day 7 - +/- 1 day	(visit 3) day 14 - +/- 1 day	(visit 4) day 28 - +/- 1 day	(visit 5) day 42 - +/- 5 day
Informed Consent	X					
Medical History and Demographics	X					
I/E Criteria	X					
Tolerability Determination for Dose Escalation			X			
Physical Exam	X	X				X
Vital Signs (Pulse, systemic blood pressure, temperature, respiratory rate and pulse oximetry)	X	X	X			X
Non-invasive blood pressure measurement		X	X			
Oxygen Saturation		X	X			
Laboratory Tests***	X					
Urine Pregnancy Test Δ	X					
Spirometry	X	X	X	X	X	X
Sputum Collection		X		X	X	X
FeNO		X	X		X	
oral wash		X		X	X	X
Percutaneous metHgb Level§		X	X		X	
CFQ-R symptom assessment		X	X	X	X	X
AE Assessment		X	X	X	X	X
Interval History Assessment						X

Δ Urine pregnancy test will be performed only on female of childbearing potential. *** Clinical laboratory tests may be repeated on study visit 1 if screen lab results deemed clinically significant and warrant repeat testing or inadvertently not collected at screen visit § Methemoglobin

(metHgb) levels: will be measured and recorded at the following time points: pre-dose, approx. 5, 15, 30, 60, and 120 minutes post each dose of nebulized sodium nitrite. If percutaneous measurements exceed 5%, then a venous blood sample will be drawn for confirmation. Peripheral blood for confirmatory methemoglobin level will be obtained 60 minutes after nebulization on study days 0 and 7 and for a final methemoglobin level on day 28.

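### The planned pre-treatment AE summary covers under three hours per subject, because AE collection starts at the visit where the first dose is given; percentages across the three AE periods are therefore not comparable

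*Combined protocol and SAP*

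**What the plan says.** Section 2.15.2 (Safety Analysis) plans tables of the number and percentage of subjects with AEs, and adds: "AEs occurring pre-treatment, during active treatment and post-treatment will be summarized separately". The same paragraph sets the collection window: "All adverse events experienced by subjects will be collected from beginning of visit 1 through final study visit". Sections 2.5, 5.5.2 and 5.5.6.1 repeat that window.

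The schedule in Section 2.11 agrees with it. The row "AE Assessment" is marked at the five visits from day 0 to day 42 and not at screening. Section 2.2.1 places screening well before Visit 1: "Screening (day -28 to -2". Section 2.10 puts consent ahead of the screening evaluations.

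The first dose falls within Visit 1. Section 2.2.1 says of that visit "This visit will take approximately 5 hours". It lists the questionnaire, vital signs, physical examination, sputum, oral wash, exhaled NO and spirometry, then continues: "Next, an electronic nebulizer will be used to deliver 45 mg of nebulized sodium nitrite". After the dose, "Subjects will be monitored closely for the next two hours". Section 2.4 gives 14 days, with a 5-day window either way, of follow-up after treatment ends.

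**The concern.** The plan promises a three-column AE summary, and its own collection rule leaves one column almost without observation time. The trial is open label with a single treated group, and its first aim is safety. Section 2.15.1 names cough and changed respiratory symptoms as the main AEs in CF antibiotic trials, with discontinuation for them in placebo as well as treatment arms. A reader will naturally set the on-treatment column beside the pre-treatment one. A near-empty column next to a full one would look like a drug effect even if the underlying event rate never changed.

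The little time that is covered is not a clean baseline either. Subjects who cannot expectorate have hypertonic-saline induction before dosing at Visit 1. Section 5.1.3 lists coughing, wheeze, chest tightness and shortness of breath among its effects. Events after consent but before Visit 1 are not collected as AEs at all.

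**Working it through.** The plan gives no figure for the length of its AE periods. Its one computed figure, 33 subjects for 82% power, reproduces: an exact one-sided binomial test of 0.06 against 0.20 that rejects at 5 or more events has alpha 0.0454 and power 0.818. It uses no AE rate, so nothing below changes it.

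**Inputs**
- Visit 1 length: about 5 h (Section 2.2.1).
- Post-dose monitoring: 2 h (Section 2.2.1).
- Nebulization: "It is anticipated that each nebulization will take approximately 10" to 15 minutes (Section 2.7.4).
- Treatment: 1 week plus 3 weeks = 28 days (Section 2.2.1).
- Follow-up: 14 ± 5 days (Section 2.4).
- Subjects: 35.

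**Pre-dose time per subject**, taken as visit length minus monitoring minus nebulization:
- 5 h − 2 h − 10 min = 2.83 h
- 5 h − 2 h − 15 min = 2.75 h

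This is an upper limit, since it treats all remaining visit time as falling before the dose.

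**Observation time for 35 subjects, all completing**
- Pre-treatment: 35 × 2.83 / 24 = 4.1 subject-days
- Treatment: 35 × 28 = 980 subject-days
- Follow-up: 35 × 14 = 490 subject-days (35 × 9 = 315 to 35 × 19 = 665)
- Treatment to pre-treatment: 28 × 24 / 2.83 = about 237 to 1

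The synopsis gives 56 days of treatment where the design section gives four weeks. The two must be reconciled before the active and post-treatment periods can be defined. With 56 days the treatment total would be 35 × 56 = 1,960 subject-days, and the imbalance would be larger.

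**What unequal windows do to percentages.** Assume one constant AE rate *r* per subject per 28 days in all periods, so no drug effect. The rate is not in the documents; the range 0.5 to 3 is an assumption. Expected subjects with at least one AE in a window of *d* days = 35 × (1 − exp(−*r d* / 28)).

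| *r* | Pre-dose, 2.83 h | Treatment, 28 d | Follow-up, 14 d |
|---|---|---|---|
| 0.5 | 0.07 | 13.8 | 7.7 |
| 1 | 0.15 | 22.1 | 13.8 |
| 2 | 0.29 | 30.3 | 22.1 |
| 3 | 0.44 | 33.3 | 27.2 |

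At *r* = 1 the three columns would read about 0.4%, 63% and 39% (0.15, 22.1 and 13.8 of 35) with no drug effect at all.

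**After extending collection to screening.** The nominal pre-treatment period becomes 2 to 28 days per subject: 35 × 2 = 70 to 35 × 28 = 980 subject-days, or 10 to 140 person-weeks. Today it is 4.1 / 7 = about 0.6 person-weeks.

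**The case against.** A reader might infer that the pre-treatment period is the sole within-subject comparator, or the sole means of separating background illness from drug. The documents do not support either reading. The sentence on separate summaries also names a post-treatment period, which is off drug for about 14 days and has an AE assessment at day 42. The plan also has a CFQ-R before the first dose and at every later visit (Sections 2.2.1 and 2.11), with a 4.0-point threshold for meaningful change (Section 2.12.5). It has pre-dose spirometry, a causality assessment for AEs (Section 5.5.6.4) and a separate summary of drug-related AEs (Section 2.15.2). No section plans a formal comparison of AE rates between periods.

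Separating pre-dose events at Visit 1 also has a sensible use: it keeps induction symptoms out of the on-treatment count.

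A screening baseline would be imperfect too:
- Entry criteria exclude recent hospitalization, additional antibiotics or steroids, and changes in maintenance therapy. Enrolled subjects were therefore selected for stability, which may bias the background rate low.
- For users of inhaled antibiotics, Visit 1 falls 2–7 days after the next scheduled antibiotic starts. Screening time may precede that start; treatment time does not.
- No visit lies between screening and Visit 1, so events would rest on recall of up to 28 days.

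All of this stands, and it limits how the extra data may be used. It does not remove the mismatch between the promised summary and the collection window. The follow-up period is not a clean substitute: events can carry over from treatment, it always comes last, and withdrawn subjects are only encouraged to attend (Section 2.14.1).

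**Conclusion.** The point holds in a limited form. The only pre-dose AE period is at most about 2.8 hours per subject, about 4 subject-days in total, against about 980 on treatment and about 490 in follow-up. It may largely reflect sputum induction. The planned numbers and percentages are not comparable across the three windows.

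The size rests on the approximate visit and nebulization times, on 28 days of treatment, and on all 35 subjects completing. Early stopping would shorten the treatment total but leave the contrast overwhelming. The expected counts rest on an assumed constant AE rate and are illustrative only.

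It does not follow that the trial lacks any means of judging AEs, or that its primary analysis is affected. FEV₁, the sample size and the power stand as they are. Severity is low: worth changing because it is cheap.

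**What to change.** **Preferred.** Collect AEs from consent, by asking at the existing Visit 1 about events since screening. Amend the collection window in Sections 2.5, 2.15.2, 5.5.2 and 5.5.6.1, and annotate the Visit 1 entry in Section 2.11. In Section 2.15.2, define the period boundaries by first and last dose, and report AEs per person-week by period alongside the percentages. List the pre-dose hours of Visit 1 separately so that induction effects stay visible.

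Present the pre-treatment rate as descriptive only, and state its limits: variable screening length (2–28 days), recall over up to 28 days with no visit in between, selection of subjects stable at enrolment, and a possible difference in inhaled-antibiotic timing between screening and treatment.

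**If collection is not extended.** Drop the pre-treatment rate summary and label the pre-dose Visit 1 events as procedure-related, that is, arising around the visit's procedures. Person-week rates are still worth reporting for the treatment and follow-up periods.

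**Cost.** A few more AE worksheet entries and a text amendment. No new visit, and no change to the sample size.

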4. Elevated percutaneous methemoglobin levels measured by pulse co-oximeter will be continuously monitored and confirmed by venous methemoglobin level. Follow up will be based upon the clinical decision of the operating physician and will be documented as such.
5. A single occurrence of venous methemoglobin levels >5% in an individual subject will result in no further dosing for that individual subject for the remainder of the study period.
6. Common Terminology Criteria for Adverse Events v. 4.0 ([CTCAE](#)). CTCAE criteria will be applied if considered related to study drug and confirmed on repeat testing.

2.4 DURATION OF FOLLOW-UP: All subjects will be followed for 14 days +/- a 5 day window after completion of the study treatment. Subjects removed from study for unacceptable adverse events will be followed until resolution or stabilization of the adverse event.

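### AE percentages are summarised over periods of a few hours, 28 days and 14 ± 5 days without time at risk, so the on- and off-treatment figures are not on a common scale

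*Combined protocol and SAP*

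**What the plan says.** Section 2.15.2 gives the AE statistic as "The number and percentage of subject experiencing at least one AE of any type", repeated by body system and preferred term. It closes by saying that "AEs occurring pre-treatment, during active treatment and post-treatment will be summarized separately". That closing sentence does not name a statistic. The natural reading is that the same counts and percentages are given for each period.

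The period lengths come from elsewhere in the document:

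- **Pre-treatment.** Section 2.15.2 states "All adverse events experienced by subjects will be collected from beginning of visit 1 through final study visit", so screening is not covered. On visit 1 (section 2.2.1): "This visit will take approximately 5 hours. Subjects will arrive and complete the CFQ-R CF Questionnaire". After the dose, "Subjects will be monitored closely for the next two hours".
- **Active treatment.** Section 2.2.1: "The starting dose of nebulized sodium nitrite is 45 mg for the first week", followed by the "escalation target dose of 90 mg for the remaining three weeks of the study". The synopsis gives the duration of treatment as 56 days.
- **Post-treatment.** Section 2.4: "All subjects will be followed for 14 days +/- a 5 day window after completion of the study treatment".

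The schedule in section 2.11 places AE assessments on Days 0, 7, 14 and 28, and then once more on Day 42. No section plans a rate per subject-time, an exposure column or windows of equal length.

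**The concern.** The percentage of subjects with at least one AE is cumulative and rises with the time over which subjects are watched. Columns for hours, four weeks and about two weeks will therefore differ even if the drug does nothing. More frequent questioning on treatment may widen the gap through better recall.

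The trial is open-label with no control arm, and safety is its objective. Section 2.15.1 itself reports that cough and respiratory symptoms led to discontinuation in placebo arms as well as active arms of comparable studies, so a background of such events is expected. The off-drug period is the nearest thing in the trial to a reference for that background. Side-by-side percentages invite a comparison that they cannot support. An excess on treatment could be read as a drug effect when it only reflects the longer period.

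**Working it through.** **The plan's own figure.** The only power figure in section 2.15 is 82% with 33 subjects, for 0.06 against 0.20, one-sided 0.05. It reproduces: rejecting at 5 or more of 33 gives an exact alpha of 0.0454 and power of 0.8179. It concerns discontinuation, and nothing below depends on it.

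**Inputs**

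- Pre-treatment: about 5 h for the visit minus 2 h of post-dose monitoring, so at most about 3 h = 0.125 day.
- Active treatment: 7 + 21 = 28 days (section 2.2.1).
- Post-treatment: 14 days, range 14 − 5 = 9 to 14 + 5 = 19 (section 2.4).
- AE rate: not given, so a range is assumed.

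**Model.** The hazard λ is constant and the same on and off drug, with no carry-over. Then P(at least one AE in d days) = 1 − exp(−λd). Write p14 for the 14-day value, so exp(−14λ) = 1 − p14.

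**Ratio with 14 days of follow-up.** (1 − exp(−28λ)) / (1 − exp(−14λ)) = 1 + exp(−14λ) = 2 − p14.

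| p14 | P over 28 days | Ratio, 14 days off | Ratio, 9 days off | Ratio, 19 days off |
|---|---|---|---|---|
| 5% | 9.8% | 1.95 | 3.01 | 1.45 |
| 10% | 19% | 1.90 | 2.90 | 1.43 |
| 30% | 51% | 1.70 | 2.49 | 1.33 |
| 50% | 75% | 1.50 | 2.09 | 1.23 |
| 80% | 96% | 1.20 | 1.49 | 1.08 |

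As the rate tends to zero, the ratio tends to the ratio of lengths: 28/14 = 2.0, 28/9 = 3.1, 28/19 = 1.5.

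**In subjects out of 35.** At p14 = 10%: 35 × 0.19 = 6.65 on treatment against 35 × 0.10 = 3.5 after it. At p14 = 50%: 26.25 against 17.5.

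**Pre-treatment column.** Over 0.125 day the probability is 0.09% at p14 = 10% and 0.6% at 50%. The column will be practically empty.

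**Early removal.** Suppose 10% stop at Day 7, the upper end of the range that section 2.15.1 expects for FEV1. If all subjects have 14 days off drug, the ratio is 1.76 at p14 = 10% and 1.41 at 50%. If the removed subjects are followed to Day 42 (35 days off), it is 1.56 and 1.32.

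**If treatment lasted 56 days.** The low-rate limit would be 56/14 = 4.0, and 3.44 at p14 = 10%.

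**On a subject-time scale.** AEs per subject-day have expectation λ in both periods, a ratio of 1.0. For subjects with an AE, the denominator must stop at each subject's first AE in the period. Dividing by full period length would over-correct: (P28/28) / (p14/14) = (2 − p14)/2, which is 0.95 at p14 = 10% and 0.75 at 50%.

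**The case against.** The strongest reply is that the plan never proposes to compare the columns. The periods are to be summarised separately, with no test or decision rule, and their nominal lengths are stated, so a careful reader can allow for them. This stands, and it limits the harm to interpretation. It does not make the columns comparable. Nominal lengths are also not actual time at risk when follow-up can vary from 9 to 19 days and removed subjects are encouraged to keep attending (section 2.14.1).

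The trial also has other safety evidence: FEV1 before and after observed doses (section 2.13.1), drug-related AEs and AEs leading to withdrawal (section 2.15.2), and a causality assessment of AEs (section 5.5.6.4). This stands too. The safety conclusion does not rest on these columns alone, although causality in an open-label trial is an unblinded judgement.

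Three stronger readings are tempting, and the documents do not support them:

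- **A reader might infer that an inert drug will always show nearly twice as many affected subjects on treatment.** That holds only for infrequent AEs with 14 days of follow-up. For any AE at all, p14 may be high and the ratio much nearer 1.
- **A reader might infer that early removals hide harm by shortening active time.** For the any-AE count this mostly fails. Section 5.5.6.3 counts a test finding that leads to a dosing change or discontinuation as an AE, so such a subject is already counted. Only other preferred terms could be affected.
- **A reader might infer that Days 14–28 against Days 28–42 is a clean contrast.** It omits first-dose and escalation effects, loses subjects removed earlier, and still carries the ± 5-day window of visit 5.

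**Conclusion.** The point holds as a weakness in how the AE tables can be read. With equal hazard on and off drug, the active-treatment percentage exceeds the 14-day post-treatment percentage by construction: by about 1.9 to 2.0 times for infrequent AEs, 1.5 times at p14 = 50% and 1.2 times at 80%. At low rates, the follow-up window alone moves the factor between about 3.1 and 1.5. The pre-treatment column carries almost no information.

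These sizes rest on a constant hazard, no carry-over, 28 days of treatment and assumed AE rates. They also assume that the subject percentages in section 2.15.2 are what will be shown by period. The FEV1 endpoint and its test are unaffected. This is a cheap improvement to a descriptive method and does not invalidate the safety assessment.

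**What to change.** In section 2.15.2, for each period and beside the crude percentages, add:

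1. Total subject-days at risk, with the active period ending at last dose and the post-treatment period ending at last contact.
2. AEs per subject-week, with a 95% confidence interval that allows for repeated events in one subject.
3. Subjects with at least one AE per subject-week, with a 95% confidence interval, each subject's time stopping at the first such AE in that period.
4. A statement that crude percentages are not to be compared across periods.

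Average rates dilute acute reactions over four weeks, so events during the observed doses on Day 0 and Day 7 should still be shown separately. A Days 14–28 against Days 28–42 display may be added as a supplement only, with its omissions stated.

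The 56-day duration in the synopsis and the 28 days in section 2.2.1 must be reconciled before the denominators are defined.

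The cost is SAP wording and an extra column or so per AE table. It needs dose, visit and AE onset dates that the trial should already hold, and no new assessments.
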